8.1. Study Design

This study is a retrospective, observational medical record review of adult patients with metastatic RCC. A sample of 150 records of patients who meet the eligibility criteria described in [Section 8.2.1](#) will be targeted. Data describing patient and clinical characteristics, first-line treatment patterns, AEs, and clinical outcomes will be abstracted directly by the PI and/or their designated research team. This study is descriptive, with the primary goal of retrospectively summarizing existing sunitinib treatment patterns and patient outcomes. As the data collected will be retrospective, the conduct of this study will in no way influence prescribed treatment. [Figure 2](#) presents a graphical summary of the study design for patients who switched from the 4/2 to 2/1 schedule. [Figure 3](#) displays a summary of the study design for the sample of patients in Brazil who initiated first-line sunitinib on the 2/1 schedule.

The primary measures of interest are described in [Section 8.3](#).

Figure 2. Study Design: First-Line Switch From 4/2 to 2/1 Sunitinib

[figure not shown]

RCC = renal cell carcinoma.

Note: The end of study follow-up may be contingent on country-specific or site-specific ethics requirements, for example, the last date of available data on the date of ethics approval at a given site. Patients may have a gap between stopping the 4/2 schedule and starting the 2/1 schedule.

PFIZER CONFIDENTIAL

Figure 3. Study Design: Initiated First-Line 2/1 Sunitinib (Brazil Only)

RCC = renal cell carcinoma.

Note: The end of study follow-up may be contingent on country-specific or site-specific ethics requirements, for example, the last date of available data on the date of ethics approval at a given site.

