8.2.1. Patient Inclusion Criteria

1. Diagnosed with metastatic RCC with clear cell histology:
 - a. The patient may have been initially diagnosed with Stage IV or initially diagnosed at an earlier stage and progressed to having disease at distant sites (ie, metastatic disease).
2. Initiated first-line treatment for metastatic RCC with sunitinib on the 4/2 schedule (all countries) or initiated first-line treatment for metastatic RCC with sunitinib on the 2/1 schedule (Brazil only).
3. Switched to the 2/1 schedule (all countries) or initiated the 2/1 schedule (Brazil only) during the first treatment line between January 1, 2014, and June 30, 2018:
 - a. The final dates defining this selection period will be dependent on country-specific ethics and reporting requirements.
4. Aged 18 years or older at the time of the switch to the 2/1 schedule (all countries) or initiation of the 2/1 schedule (Brazil only).

PFIZER CONFIDENTIAL

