8.3.4. Treatment-related Outcomes

Treatment-related AEs (eg, hypertension, neutropenia, thrombocytopenia, fatigue, stomatitis) will be documented for the duration of first-line treatment with sunitinib. Frequency of toxicity evaluation (eg, every 6 weeks) and the method of evaluation (eg, radiological evaluations by computed tomography, magnetic resonance imaging with measurable lesions via Response Evaluation Criteria in Solid Tumors [RECIST]) will also be documented.

Dates of progression and death (ie, whether the patient died during the follow-up period and whether the death was related to RCC) will be documented. Disease progression and survival estimates will be derived from these measures and calculated from the date of diagnosis of metastatic RCC, the start of first-line treatment line with 4/2 or 2/1 sunitinib, and the time of switch to the 2/1 schedule (among those who initiated on the 4/2 schedule). Survival estimates will include, but are not limited to, the following:

[figure not shown]
- Overall survival;
- PFS;
- Time to second-line initiation.

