8.7. Data Analysis

All measures described in [Section 8.3](#) will be summarized descriptively through the tabular and graphical display of mean values, medians, ranges, and standard deviations of continuous variables of interest and frequency distributions for categorical variables. Time-to-event outcomes (ie, overall survival, PFS, time to second-line initiation) will be described using the Kaplan-Meier method. All analyses will be conducted using SAS (version 9.4 or later) statistical software. Samples of patients who switched from the 4/2 to the 2/1 schedule from each country will be pooled and analyzed in aggregate. The sample of patients from Brazil who initiated first-line sunitinib on the 2/1 schedule will be analyzed separately. Results may be described for up to 2 subgroups that will be determined after the initial review of the data (eg, number of cycle on the 4/2 schedule).

As this study is descriptive and designed to generate hypotheses, direct comparisons between outcomes on the 4/2 schedule and on the 2/1 schedule will not be conducted. Potential confounders, such as characteristics that prompt the switch and other possible time-dependent factors (eg, dose modifications and delays), are not comprehensively collected or controlled for in this study design. Variability in timing of the switch from a 4/2 to a 2/1 schedule will affect the distribution of time-dependent outcomes after the switch (even in the absence of immortal-time bias), as some patients may switch “early” in their first-line therapy and others may switch “later.” Thus, causal inferences about the benefit of switching treatment schedules cannot be drawn.

PFIZER CONFIDENTIAL

Detailed methodology for summary and statistical analyses of data collected in this study will be documented in a statistical analysis plan, which will be dated, filed and maintained by the sponsor. The statistical analysis plan may modify the plans outlined in the protocol; any major modifications of primary endpoint definitions or their analyses would be reflected in a protocol amendment.

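### Kaplan-Meier is assigned to time to second-line initiation with no rule for death before second line; if deaths are censored, the curve overstates the probability of starting second line

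*Combined protocol and SAP*

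**What the plan says.** Section 8.7 (Data Analysis) groups three outcomes under one method: "overall survival, PFS, time to second-line initiation) will be described using the Kaplan-Meier method". Section 8.3.4 (Treatment-related Outcomes) introduces its list with "Survival estimates will include, but are not limited to, the following" and gives the third item simply as "Time to second-line initiation". It states no event definition, censoring rule or treatment of death for that item.

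The information needed is collected. Section 8.3.4 records "Dates of progression and death (ie, whether the patient died during the follow-up period and whether the death was related to RCC"), and section 8.3.3 records the start and stop dates of every treatment line and the date of the switch to, or start of, the 2/1 schedule.

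Several time origins are planned. Progression and survival estimates are "calculated from the date of diagnosis of metastatic RCC, the start of first-line treatment line with 4/2 or 2/1 sunitinib", and also from the switch for patients who began on 4/2. Eligibility in section 8.2.1 requires that patients "Switched to the 2/1 schedule (all countries) or initiated the 2/1 schedule (Brazil only) during the first treatment line".

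Section 8.7 leaves detailed methodology to a statistical analysis plan, which may modify the protocol. The combined document contains no text of that plan. The abstract's own Kaplan-Meier list names overall survival, treatment duration and PFS, and omits second-line initiation.

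**The concern.** For overall survival death is the event, and for PFS it is ordinarily part of the event. Second-line initiation is different: a patient who dies on or after first line without further treatment can never start second line. The name of the endpoint contains one event only. A programmer given that name and the instruction to use Kaplan-Meier would ordinarily censor the deaths.

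Kaplan-Meier treats a censored patient as still able to have the event later, at the same rate as those who remain under observation. For the dead that is false, so one minus Kaplan-Meier exceeds the proportion who actually start second line. If the programmer counts deaths as events instead, the curve is valid but describes second line or death, which is a different quantity. Two analysts could both follow section 8.7 and report different results under the same label.

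At stake are this one curve, its percentages at fixed times and its median. Section 6 offers the study's results as baseline measures for later comparison, so a mislabelled percentage could be carried forward.

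**Working it through.** The documents give no figure for this endpoint, so there is nothing to reproduce. The calculation below shows size only.

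**Inputs**
- Median time *m* to leaving first line, by second line or death: 11 months, borrowed from the sunitinib PFS in section 6, or 18 months. Both are assumptions; neither is documented for this endpoint.
- Share *p* of those exits that are deaths: 5, 10, 20, 30, 40 or 50%. Assumed; the documents give none. Section 6 cites a median overall survival of 26.4 months on sunitinib, so deaths cannot be presumed rare.
- Constant hazards, λ = ln 2 / *m*. Assumed.

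**Formulas**
- Deaths censored: 1 − KM(*t*) = 1 − exp(−(1−*p*)λ*t*)
- Cumulative incidence of second line: (1−*p*)(1 − exp(−λ*t*))
- Second line or death: 1 − exp(−λ*t*)

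**Worked case**, *m* = 11, *p* = 30%, *t* = 24: λ*t* = 24 × 0.6931 / 11 = 1.512.
- Deaths censored: 1 − exp(−0.7 × 1.512) = 65.3%
- Cumulative incidence: 0.7 × (1 − exp(−1.512)) = 54.6%
- Excess: 10.7 points
- Second line or death: 78.0%

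The times at which these three curves reach 50% are 15.7, 19.9 and 11 months. A simulation of 2,000 samples of 150, with censoring uniform over 12 to 60 months, gave 65.4% and 54.7% for the first two at 24 months, in agreement with the formulas.

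**Excess of one minus Kaplan-Meier over cumulative incidence, in percentage points**

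| Death share *p* | 5% | 10% | 20% | 30% | 40% | 50% |
|---|---|---|---|---|---|---|
| *m* = 11, 12 months | 0.8 | 1.6 | 2.9 | 4.0 | 4.6 | 5.0 |
| *m* = 11, 24 months | 2.2 | 4.2 | 7.8 | 10.7 | 12.9 | 14.1 |
| *m* = 18, 12 months | 0.4 | 0.7 | 1.3 | 1.7 | 2.0 | 2.1 |
| *m* = 18, 24 months | 1.1 | 2.2 | 4.0 | 5.4 | 6.4 | 6.8 |

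**Against sampling error.** The 95% half-width of the 24-month cumulative incidence, 1.96 × √(CIF(1−CIF)/*n*), without censoring and over both medians, is 7.0 to 8.0 points at *n* = 150 and 8.6 to 9.8 at *n* = 100. The smaller *n* is relevant because the target is "A sample of 150 records of patients who meet the eligibility criteria", which covers both groups, while "The sample of patients from Brazil who initiated first-line sunitinib on the 2/1 schedule will be analyzed separately". The excess clearly passes the half-width only with the 11-month median and a death share of 30% or more. With the 18-month median it never does. Real half-widths will be wider because follow-up is censored.

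**The case against.** **Deferral to the analysis plan.** Censoring rules normally belong in a statistical analysis plan, and section 8.7 says that one will be written. This stands in part. A reader might infer that the final analysis is wrong. The documents do not show that: they show a gap in the protocol, and the heading over the endpoint list, "Survival estimates will include, but are not limited to, the following", is a weak hint that death might be counted. But the protocol has already named a method, and on its ordinary reading that method is biased for this endpoint.

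**Size and importance.** The 11-month anchor is PFS from a trial in another population. Section 6 cites a registry with much longer treatment on 2/1, which favours the longer median and so the smaller excess. Section 7 warns of limited follow-up, and at 12 months the excess is at most 5.0 points. The endpoint is in no stated objective. The number of systemic lines will be tabulated, so a crude share receiving second line will be visible, although that share does not allow for unequal follow-up. All of this stands and limits the weight of the point.

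**Time origin.** Switchers cannot die or start second line before the switch. A reader might therefore infer that curves from metastatic diagnosis or from 4/2 start are biased and need delayed entry. The documents do not support that remedy.
- *From diagnosis.* A patient not yet on first line cannot start second line. Delayed entry would give that period the hazard of patients already on 2/1. Take Brazil initiators with *m* = 11, *p* = 20% and time from diagnosis to 2/1 start uniform over 0 to *a* months (assumed). The true 24-month value is 0.8 × [1 − exp(−24λ)(exp(λ*a*) − 1)/(λ*a*)], which is 60.6, 58.6 and 53.6% for *a* = 3, 6 and 12. Delayed entry targets 0.8 × (1 − exp(−24λ)) = 62.4%, about 2 to 9 points too high.
- *From 4/2 start.* The uncorrected curve is too low only as an estimate for everyone who starts 4/2. Section 7 sets out to describe patients who switched, and for them it is a valid conditional description. Delayed entry also needs switch timing to be unrelated to later exit, whereas sections 8.7 and 8.9 say that the characteristics prompting the switch are neither fully collected nor controlled. A clear label is enough.

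**Conclusion.** The point holds as a gap with a predictable direction. Section 8.7 names Kaplan-Meier for an endpoint that death can preclude, and the documents give no rule for death. If deaths are censored, the probability of starting second line is overstated whenever any patient dies first.

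How far is unknown. The range of about 2 to 14 points (11-month median) or 1 to 7 points (18-month median) at 24 months rests entirely on assumed constant hazards, assumed medians and assumed death shares of 5 to 50%. Over much of that range the excess is within sampling error.

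A reader might extend the criticism to overall survival and PFS because they share the same sentence. The competing-risk argument does not reach them. The correction is worth making because it is cheap, not because the study's conclusions hang on it.

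**What to change.** In section 8.7 and the statistical analysis plan, adopt one of two options:

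1. Report the Aalen-Johansen cumulative incidence of second-line initiation, with death before second line as the competing event. Censor patients who are alive without second line at their last available record.
2. Rename the endpoint time to second-line initiation or death in sections 8.3.4 and 8.7, and keep Kaplan-Meier.

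Under either option, make the main curve start at the switch to 2/1 for switchers and at 2/1 start for the Brazil initiators. Label any switcher curve from an earlier origin as conditional on having reached the switch during first line. Do not require delayed entry.

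The cost is two or three sentences and slight extra programming, with no new data. Section 8.7 lets the analysis plan modify the protocol and ties amendments to major changes in primary endpoint definitions or analyses, so an amendment does not appear to be needed. Under the first option, the reported probability of starting second line will be lower than a curve that censors deaths would show.

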8.8. Quality Control

The following data checks will be performed for all data collected in the eCRF:

- Check for illogical or unusual data (eg, treatment starting prior to diagnosis);
- Check for speeders (ie, abstractors who seem to skim through the eCRF by falling below a certain tolerance time interval of an estimated average duration needed for completing the form);
- Check for responders with a typical unrealistic response pattern, such as always checking the same value in a numerical scale or responding in an erratic, implausible manner to certain questions;
- Check for an extremely high percentage of “Do not know” or “Data not available” responses;
- Check for an extremely high percentage of answering filter questions in a way so as to avoid having to answer subsequent questions in more detail.

The **PPD** Office of Quality Assurance (OQA) is an independent unit that reports to the Vice President of **PPD** and provides training on applicable regulations and guidelines, implements and maintains a series of standard operating procedures, and provides quality assurance monitoring for compliance with regulatory requirements.

PPD will work closely with the selected subcontractors to establish and ensure a complete integration of procedures for the project. The OQA will perform audits and assessments that involve various aspects of the project for involved subcontractors, including but not limited to, education and training documentation. Audits are conducted by the OQA according to established criteria in standard operating procedures and other applicable procedures. The OQA reports quality assurance observations to the Project Director and facilitates corrective actions, if necessary.

8.9. Limitations

Retrospective medical record reviews are subject to the following general limitations:

- Patients selected for study inclusion represent a “convenience” sample, in that the records will be obtained from sites who are willing to participate in the study. Therefore, study findings may not be generalizable to the overall population of patients with metastatic RCC or sites where RCC is treated in the selected countries.
- All data captured in the eCRF will be limited to information available in the patients’ medical records held by the sites participating in the study. Information on health care services received outside the sites’ care setting that is not recorded in the medical record will be unavailable for this study (eg, treatment for AEs received through a separate hospital).
- To increase the chance of random selection of eligible medical records at sites that estimate a larger than needed eligible population, abstractors will be asked to select medical records for patients whose last names begin with a randomly generated letter between A and Z. Due to variations in the distribution of first letters among last names, patients may not have an equal probability of inclusion in the study.
- Data will be entered directly by each site’s research team or PI and therefore may be subject to entry errors and resulting inaccuracies in reporting. Although there will be data checks in place to improve internal consistency of the data, responses will not be validated against the patients’ medical records by an independent reviewer.
- This study is designed to describe characteristics and outcomes of patients who switched from the 4/2 to the 2/1 sunitinib schedule. Potential confounders, such as characteristics that prompt the switch and other possible time-dependent factors (eg, dose modifications and delays), are not comprehensively collected or controlled in this study design. Variability in timing of the switch from a 4/2 to a 2/1 schedule will affect the distribution of time-dependent outcomes after the switch (even in the absence of immortal-time bias), as some patients may switch “early” in their first-line therapy and others may switch “later.” Thus, causal inferences about the benefit of switching treatment schedules cannot be drawn.

8.10. Other Aspects

Not applicable.

9. PROTECTION OF HUMAN SUBJECTS

9.1. Patient Information

The PIs at each site will be provided with a summary of the protocol, objectives, and methods as well as their rights and responsibilities prior to providing their consent to participate in the study. Physician or participating site staff's consent will be obtained electronically prior to participating in the medical record abstraction.

Patient medical record data may contain highly sensitive and private personal health information. Therefore, the following data collection strategies will be implemented to ensure the data collected in this study strictly comply with definitions of deidentified or anonymous data:

- At any point in this study, members of the PI's direct health care team or designated research team are the only individuals with access to the patient's medical record data containing potentially identifiable information. The study team (ie, PPD and Pfizer) will not view, obtain, or have access to any identifiable health information such as patient name, address, date of birth, or other personal identifiers.
- Patient identifiers such as name, address, telephone number, e-mail address, health record/beneficiary number, biometric data, and photographs are not relevant to this study and will not be collected or viewed at any point by the study team.

As the data used in this study are anonymous, this study poses minimal risk to patients whose medical record data are analyzed. With anonymous data, the risk of a breach of confidentiality is primarily from malicious system hacking in the presence of suboptimal network security in the case of electronic data collection. Outside of network security risks, identification of a single patient by members of the research investigative team, based on a combination of limited demographic information and treatment information, would require (in addition to malicious intent) access to all medical records in a region (including those outside the physicians/sites participating in the study) and an extraordinary analytic effort, except, perhaps, in the case of exceedingly rare conditions, which the current study does not include. Based on the study design and data collection procedures, the study team believes there is only a minimal/remote risk of identification of patients.

The PI's in this study will be subject to different, albeit remote, risks compared with patients. It is conceivable that participation in the study may divert a small amount of the physicians' time and resources away from clinical activities to allow for their participation in this research. However, it is expected that these physicians will adequately manage their time.

Only the abstractors who directly enter the patient data into the secure eCRF will see explicit patient identifying information. The web portal used for data collection is hosted in a secure data center. This data center offers a secure environment that minimizes the chance of a security breach, thereby allowing access only to authorized persons with valid usernames and passwords. Only anonymized data will be held at the data center. As stated previously, to

protect the rights and freedoms of natural persons with regard to the processing of personal data, no protected health information will be collected, and thereby, no data containing patient identifiable information will be transferred to Pfizer.

All parties will comply with all applicable laws, including laws regarding the implementation of organizational and technical measures to ensure protection of patient personal data. Such measures will include omitting patient names or other directly identifiable data in any reports, publications, or other disclosures, except when required by applicable laws.

9.2. Patient Consent

As this study does not involve data subject to privacy laws according to applicable legal requirements, obtaining informed consent from patients by Pfizer is not required. If ethics requirements at a participating site or in a given country require informed consent, a waiver of informed consent will be sought.

9.3. Participation Withdrawal

Participating sites may withdraw from the study at any time at their own request, or they may be withdrawn at any time at the discretion of the investigator or sponsor for safety, behavioral, or administrative reasons. If a site withdraws from the study and withdraws consent for disclosure of future information, no further evaluations should be performed, and no additional data should be collected. The sponsor may retain and continue to use any data collected before such withdrawal of consent.

